4.2.3. EXPLORATORY ENDPOINTS

Exploratory endpoints for informational purposes only:

1. Index procedure resource utilization: Anesthesia, procedure time and time to discharge.
2. Follow up resource utilization: Nasal airway obstruction related return visits and medication utilization.
3. Subject satisfaction questionnaire at 1, 3, and 12 months.
4. Degree of nasal airway obstruction as reported by subjects on the VAS scale at baseline with decongestant use.
5. Endoscopic lateral wall insufficiency score per side²¹ at baseline 1, 3, 6 and 12 months.
6. 3-D camera lateral wall motion assessment per side at baseline and 3, 6, and 12 months (at select sites).
7. Cosmesis changes from baseline evaluated by Independent Photo Review at 3 and 6 months (at select sites).
8. Change in subject sleepiness scale from baseline to 1, 3, 6, and 12 months as reported by subjects on the Epworth Sleepiness Scale (ESS).
9. Allergic rhinitis status at 1, 3, 6, and 12 months.
10. Nasal geometry: length of nose, height and width of nose, skin thickness of lateral wall at baseline.
11. Type of turbinate procedure.

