7.2.7. Baseline Nasal Exam

A Baseline Nasal Exam will be conducted for all subjects at the Baseline Visit. The exam will include collection of nasal anatomy parameters such as nose length, nose height, nose width and skin thickness.

In addition, each side of the nose will be examined with an endoscope to assess each subject's degree of inferior turbinate hypertrophy and septal deviation (superior and inferior). Each of these will be graded as Normal, Mild, Moderate, or Severe.

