10.2. STATISTICAL HYPOTHESES

Primary Efficacy Endpoint:

- The primary efficacy endpoint is the proportion of treatment responders at 6 months post procedure. Since there is no direct comparison group in this study, the primary efficacy hypothesis is a superiority comparison to a target proportion:

Null Hypothesis H_0 : the proportion of responders at 6 months is = 0.50, versus
Alternative Hypothesis H_A : the proportion of responders at 6 months is $\neq 0.50$

- There are no other formal statistical hypotheses.

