10.4.8. ADDITIONAL SUB-GROUP ANALYSES

Response percentage, change in NOSE scores and other variables including satisfaction will also be evaluated in the following subgroups:

- Turbinate reduction method - radiofrequency versus mechanical
- Time-dependent presence or absence of allergic rhinitis
- Nasal geometry factors
 - Nose length (above or below median)
 - Nose width (above or below median)
 - Categorical skin thickness

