10.4.9. MULTIPLE COMPARISON/MULTIPLICITY

No formal type 1 error adjustment will be made for the analysis of secondary and exploratory endpoints. All endpoints except for the primary endpoint should be considered supportive, and inference should be drawn with caution.

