10.5. SAMPLE SIZE

The primary study hypothesis is a superiority comparison to a target proportion:

Null Hypothesis H_0 : the proportion of responders at 6 months is =0.50, versus
Alternative Hypothesis H_A : the proportion of responders at 6 months is $\neq 0.50$

See section 10.4.2 for the definition of response. This hypothesis will be evaluated using an exact test.

In order to have $> 90\%$ power to rule out a response rate $\leq 50\%$ at a 5% (2-sided) significance level, assuming a true response rate of 66%, 150 subjects with 6 month follow-up are needed. Assuming about 10% drop-out rate, up to 170 subjects will be enrolled. All mITT subjects will be used for this comparison, regardless of protocol deviations.

The assumed response rate is the minimum value is expected to be consistent with previous trials, where an 80% response rate at 6 months was observed.

The anticipated size of the Latera stand-alone Population is 50 subjects. With only 50 subjects in this cohort, the power to reject the primary null hypothesis is approximately 63%, given a true response rate of 66%. Although this cohort is not sufficiently powered to show significance for a true response rate of 66%, the p-value and exact binomial 95% confidence interval will be calculated for this population. Retrospective power for the actual response rate will also be calculated for this comparison in order to contextualize the results.

Sample size calculations were performed using the package RCT Design for R version 3.2.3.

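### Outcome is related to nose length and width only through a median split; a continuous analysis beside it would recover precision in an exploratory question

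*Combined protocol and SAP*

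**What the plan says.** Section 10.4.8 of the protocol states: "Response percentage, change in NOSE scores and other variables including satisfaction will also be evaluated in the following subgroups". Under nasal geometry it lists "Nose length (above or below median" and "Nose width (above or below median", plus skin thickness in categories. It gives no cut-off in mm, does not name the population that supplies the median, and does not say where a value equal to the median goes. It names no test, interaction or model. No other section plans to relate outcome to length or width as measured quantities.

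On the data, section 7.2.7 says: "The exam will include collection of nasal anatomy parameters such as nose length, nose height, nose width and skin thickness". Item 10 of section 4.2.3 lists the same four baseline measures. Height is the only one without a line in section 10.4.8. Neither the unit nor the recording precision is given.

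On status, section 4.2.3 heads its list "Exploratory endpoints for informational purposes only". Section 10.2, after the primary hypothesis, adds "There are no other formal statistical hypotheses". Section 10.4.9 says: "All endpoints except for the primary endpoint should be considered supportive, and inference should be drawn with caution". Section 10.1 leaves further analysis detail to an SAP to be finalised before database lock.

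**The concern.** Length and width are measurements. A median split treats every nose on one side of the cut as alike and ignores how far each lies from it, so a gradient is estimated less precisely than the data allow.

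The question is a sensible one for this device. Section 6.2 describes a single implant length of 24 mm, and inclusion criterion 6 in section 5.1 asks for suitable nasal and facial anatomy. Readers will want to know whether benefit varies with nose size. With two halves, a real gradient is more easily missed, and curvature cannot be seen at all: poorer results at both extremes would largely average out across the halves.

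**Working it through.** **Inputs.** From section 10.5: "at a 5% (2-sided) significance level, assuming a true response rate of 66%, 150 subjects with 6 month follow-up are needed". From section 10.4.8: the cut is the sample median. Assumed: the distribution of the measure, a linear relation, and the effect sizes below. The documents give none of these.

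**Step 1. The plan's own figure.** The plan states no figure for these subgroups. Its primary power claim is reproduced only to confirm the N used here. With 150 subjects and a null rate of 0.50, the exact two-sided test rejects upward at 88 or more responders (actual alpha 0.041). At a true rate of 66% its power is 97.5%, so the stated figure of more than 90% holds. Enrolment of 150/0.9 = 167 agrees with the stated maximum of 170.

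**Step 2. Information kept by a two-group cut.** For a normal covariate with a linear effect, a cut that places proportion p on one side has efficiency φ(z)²/[p(1−p)] relative to the continuous term, where z is the cut in SD units. At the median, p = 0.5 and z = 0, so the efficiency is 0.3989²/0.25 = 0.637 = 2/π.

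- 150 split subjects are worth 150 × 0.637 = about 95 analysed continuously.
- About 150/0.637 = 236 split subjects would be needed to match 150 analysed continuously.
- A confidence interval for the same trend is wider by a factor of 1/√0.637 = 1.25.

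**Step 3. Other shapes.** The efficiency is the squared correlation between the measure and its above-median indicator.

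| Assumed distribution | Information kept |
|---|---|
| Uniform | 75% |
| Normal | 64% |
| Mildly skewed lognormal (log SD 0.15) | 62% |
| t with 5 degrees of freedom | 54% |
| Laplace | 50% |

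**Step 4. In terms of power.** Power after the split is Φ[(1.960 + z_power) × √0.637 − 1.960].

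- Continuous power 80%: Φ(2.802 × 0.798 − 1.960) = Φ(0.275) = 61%.
- Continuous power 90%: Φ(3.242 × 0.798 − 1.960) = Φ(0.626) = 73%.

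Simulation at n = 150 (10,000 runs, normal covariate) agrees. For a continuous outcome with correlation 0.226, power was 80.0% continuous and 60.4% split. For the responder outcome, with 66% response at average nose size and a logit slope of 0.5 per SD, it was 79% and 60%.

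**Step 5. Values equal to the median.** At n = 150 with an assumed SD of 2.5 to 5 mm, simulation puts 8% to 16% of subjects (about 12 to 24) exactly at the median if recording is to 1 mm, and 4% to 8% if to 0.5 mm. Much finer recording leaves almost none.

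**The case against.** The strongest reply is that nothing in the trial depends on this. Section 10.4.8 specifies no test, so the power figures measure precision and do not describe a planned comparison. Sections 4.2.3, 10.2 and 10.4.9 make these results informational and supportive. That stands, and it sets the weight of the point.

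Four stronger readings are tempting, and the documents do not support them.

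- **A reader might infer that the median split is the least efficient choice.** Under normality and linearity it is the most efficient of all two-group cuts, because the expression in Step 2 is largest at p = 0.5. It also balances the groups and, being fixed in advance, prevents choosing a cut by outcome. It loses only against a well-specified continuous term.
- **A reader might infer that a third of the information is certainly lost.** The loss depends on distribution and linearity. A true step at the median would favour the split, although nothing in the documents suggests one.
- **A reader might infer that the cut-off will be unknown to others.** Section 10.4.6 summarises baseline physical measurements, and section 10.4.1 includes the median and quartiles among the summaries, so the value in mm will be reported.
- **A reader might infer that subjects at the median are dropped.** The phrase is ordinary shorthand for two halves, and the SAP can settle the rule. How many subjects it touches depends on an unstated recording precision.

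Replacing the split by one straight-line slope would also be a poor remedy. With one implant length, misfit could arise at both extremes, and a linear term can miss that as readily as the split does. What remains is that the plan asks a reasonable question and, as written, answers it only with the less precise tool.

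**Conclusion.** The point holds as a modest improvement. Using only a median split for nose length and width keeps about 64% of the information if the measure is near normal and its effect near linear, and about 50% to 75% over the other shapes examined. At n = 150 that turns 80% power for a trend into about 60%. The distribution, linearity and effect sizes are assumptions.

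The effect is confined to exploratory, supportive results. The primary responder analysis, its hypothesis and the sample size do not use nose geometry and are unaffected. The absence of height from section 10.4.8 and the unstated handling of values at the median are minor wording matters: no section requires every recorded dimension to be a subgroup.

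**What to change.** Add to section 10.4.8, or to the SAP before database lock, text such as:

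> *Nose length, width and height will each be analysed as a continuous covariate for 6-month response (logistic regression) and for change in NOSE score (linear model). Non-linearity will be checked with a quadratic or restricted cubic spline term. The effect per mm will be reported with its 95% confidence interval, and the fitted curve will be shown where there is curvature.*

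Keep the two-group table as a descriptive display for all the variables the section already lists, satisfaction included, and label the groups as at or below, and above, the median of the mITT population. That is the population section 10.4.2 uses for the primary endpoint.

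The spline should stay simple: at 66% response, 150 subjects yield about 150 × 0.34 = 51 non-responders. The cost is a little extra analysis and reporting, with no new data, visits or procedures. The results remain exploratory under section 10.4.9.

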10.4.9. MULTIPLE COMPARISON/MULTIPLICITY

No formal type 1 error adjustment will be made for the analysis of secondary and exploratory endpoints. All endpoints except for the primary endpoint should be considered supportive, and inference should be drawn with caution.

10.4.10. TABULATION OF INDIVIDUAL RESPONSE DATA

Listings of adverse events may be produced.

10.4.11. EXPLORATORY ANALYSES

Cosmesis changes from baseline to 3 month and 6 months, evaluated by Independent Photo Review at select sites only, will also be tabulated.

Endoscopic lateral wall insufficiency score is a 3-level, categorical variable, which will be evaluated for each side separately. Baseline, 1, 3, 6 and 12 month post-baseline scores will be cross-tabulated, and the proportion with improvement will be calculated.

Response percentage, change in NOSE scores, ESS and other variables for procedures including turbinate reductions will be evaluated. Resource use will also be summarized.

10.5. SAMPLE SIZE

The primary study hypothesis is a superiority comparison to a target proportion:

Null Hypothesis H_0 : the proportion of responders at 6 months is =0.50, versus
Alternative Hypothesis H_A : the proportion of responders at 6 months is $\neq 0.50$

See section 10.4.2 for the definition of response. This hypothesis will be evaluated using an exact test.

In order to have $> 90\%$ power to rule out a response rate $\leq 50\%$ at a 5% (2-sided) significance level, assuming a true response rate of 66%, 150 subjects with 6 month follow-up are needed. Assuming about 10% drop-out rate, up to 170 subjects will be enrolled. All mITT subjects will be used for this comparison, regardless of protocol deviations.

The assumed response rate is the minimum value is expected to be consistent with previous trials, where an 80% response rate at 6 months was observed.

The anticipated size of the Latera stand-alone Population is 50 subjects. With only 50 subjects in this cohort, the power to reject the primary null hypothesis is approximately 63%, given a true response rate of 66%. Although this cohort is not sufficiently powered to show significance for a true response rate of 66%, the p-value and exact binomial 95% confidence interval will be calculated for this population. Retrospective power for the actual response rate will also be calculated for this comparison in order to contextualize the results.

Sample size calculations were performed using the package RCT Design for R version 3.2.3.

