I have received and reviewed this protocol. The trial will be carried out in accordance with this protocol and Good Clinical Practice (GCP) as required by the following:

- United States (US) Code of Federal Regulations (CFR) applicable to clinical studies (45 CFR Part 46, 21 CFR Part 50, and 21 CFR Part 56, and 21 CFR Part 812.2 (b)
- International Conference on Harmonisation (ICH) Good Clinical Practice E6
- ISO 14155:2011 Clinical investigation of medical devices for human subjects - GCP

All key personnel (all individuals responsible in the conduct of this trial) have completed Human Subjects Protection Training.

I agree to ensure that all staff members involved in the conduct of this study are informed about their obligations in meeting the above commitments.

Investigator's Printed/Typed Name

Investigator's Signature

Date

PROTOCOL SUMMARY

Title:	Spirox Latera™ Implant support of lateral nasal wall cartilage (LATERAL-OFFICE) study
Design:	A prospective, multi-center, non-randomized, single arm, controlled study
Objectives:	To obtain outcomes data in subjects with severe to extreme class NOSE scores undergoing placement of the Spirox Latera Implant with or without concurrent turbinate reduction procedures in an office setting.
Eligibility Criteria	Reference Sections 5.1 and 5.2
Primary Endpoints:	Primary Efficacy Endpoint: Proportion of treatment responders at 6 months post procedure. Responder is defined as a subject that has at least one (1) NOSE class improvement or at least 20% NOSE score reduction Primary Safety Endpoint: Nasal procedure and Latera™ device-related adverse events through 6 months
Secondary Endpoints:	
1. Proportion of treatment responders at 1, 3, 12, 18 and 24 months post procedure.2. Change in nasal airway obstruction from baseline to 1, 3, 6, 12, 18 and 24 months as reported by subjects on the VAS scale.3. Subject satisfaction questionnaire at 6 months.4. Procedure and device-related adverse events through 24 months.
Exploratory endpoints:	Reference Section 4.2.3.
Population:	Up to 250 subjects will be enrolled (includes up to 80 training subjects). At least 50 subjects will have stand-alone Latera Implant procedure.
Number of Sites:	Approximately 25 sites in the U.S.

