10.3. ANALYSES DATASETS

Four analysis populations will be considered: The analysis datasets described in the following section apply to the subjects enrolled in the main study (excluding training cases). The training subjects will not be included in the formal analyses for this protocol.

- Intention-to-Treat (ITT) Population: all enrolled subjects who began a nasal Implant procedure, regardless of concomitant turbinate treatment (i.e., Latera alone or in conjunction with turbinate treatment) or re-implant according to this protocol.
- Modified Intention-to-Treat (mITT) Population: all subjects enrolled who received at least one nasal Implant, regardless of concomitant turbinate treatment. Subjects that received a replacement implant will be included in this analysis dataset.
- Per-Protocol (PP) 6 Month Evaluable Population: subjects with 6 month post-Implant NOSE score assessments in clinic or by telephone, regardless of concomitant turbinate treatment. Subjects that received a replacement implant will not be included in this analysis dataset.
- Latera Stand-Alone Population: subjects who receive at least 1 Latera implant without concomitant turbinate treatment.

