10.4.2. ANALYSIS OF THE PRIMARY EFFICACY ENDPOINT(S)

The primary endpoint will be the proportion of treatment responders at 6 months post procedure. The mITT analysis dataset will be used to analyze the primary endpoint.

Responder is defined as a subject that has at least one (1) NOSE class improvement or at least 20% NOSE score reduction compared to baseline.

Subjects will be classified as non-responders if neither of these criteria is met.

NOSE score is a PRO instrument which measures the impact of nasal obstruction on quality of life. It is scored in increments of 5 points, and the total score is calculated as the sum of all 5 questions multiplied by 5, where the range is 0 (asymptomatic) to 100 (most extreme deleterious impact on quality of life). The NOSE score classes¹⁷ are based on the total calculated score:

- Mild:** 5 – 25 points
- Moderate:** 30 – 50 points
- Severe:** 55 – 75 points
- Extreme:** 80 – 100 points

This primary hypothesis will be evaluated for the mITT using a -2-sided exact test²³, and the corresponding exact (Clopper-Pearson) 2-sided 95% confidence interval will be calculated. The null hypothesis that the proportion of responders is $\neq 0.5$ will be rejected if the p-value is < 0.05 .

Sensitivity analyses will be conducted to determine the impact of missing data on these results. These analyses will depend on the extent of missing data, and will be detailed in the SAP, but may include:

1. Last observation carried forward (LOCF)
2. Subjects with missing data classified as non-responders
3. Re-implanted subjects classified as non-responders

This analysis will be repeated for the Latera stand-alone Population alone. While this study is not sufficiently powered to reject the null hypothesis for this subgroup, the response rate, 95% confidence interval and p-value will be calculated. See section 10.5 for further details.

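### Stand-alone cohort: the stated power of about 63% at 50 subjects does not match the planned exact test, which has 56.5%

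*Combined protocol and SAP*

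**What the plan says.** Section 10.5 sets the primary hypothesis as a response rate of 0.50 at 6 months against any other value, at a two-sided 5% level, and states the method: "This hypothesis will be evaluated using an exact test". Section 10.4.2 specifies a two-sided exact test with a Clopper-Pearson 95% interval and rejection at p below 0.05. For the cohort without turbinate reduction it adds: "This analysis will be repeated for the Latera stand-alone Population alone".

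On the size of that cohort, section 10.5 says: "The anticipated size of the Latera stand-alone Population is 50 subjects". The Protocol Summary puts it as a minimum: "At least 50 subjects will have stand-alone Latera Implant procedure". Section 10.3 defines the population as "subjects who receive at least 1 Latera implant without concomitant turbinate treatment", that is, by treatment received and not by having a 6-month score.

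On power, section 10.5 says that with 50 subjects "the power to reject the primary null hypothesis is approximately 63%, given a true response rate of 66" per cent. It acknowledges that this is not sufficient, and then adds: "Retrospective power for the actual response rate will also be calculated for this comparison in order to contextualize the results".

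For the main cohort the same section asks for 150 subjects with 6-month follow-up and allows for losses: "Assuming about 10% drop-out rate, up to 170 subjects will be enrolled".

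**The concern.** A power figure should describe the test that will be run at the sample size that is named. Here the test is exact and the number is 50, yet the 63% looks like the result of a large-sample formula. With 50 binary outcomes an exact test is conservative, because the rejection region moves in whole subjects, so the two methods can differ by several points.

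There is a second gap. The 150 in the main cohort is explicitly a number with 6-month data, whereas the 50 is not, and the population definition and the Protocol Summary both describe treated subjects. If the 50 are counted before drop-out, the power for the evaluable subjects is different again.

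The stakes are limited but real. This is the only one of the four analysis populations in section 10.3 that is restricted to the implant without concurrent turbinate reduction, and a p-value will be calculated for it. A reader judging a non-significant result there should know how likely that result was.

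**Working it through.** **Inputs.** n = 50, null rate 0.50, true rate 0.66, two-sided 5% level (all section 10.5); exact test with Clopper-Pearson interval and rejection at p < 0.05 (section 10.4.2).

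**1. Reproducing the plan's figure.** The one-sample normal approximation, with null variance for the critical value and alternative variance for power, is

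Φ( (0.16 − 1.96 × √(0.25/50)) / √(0.66 × 0.34/50) ) = Φ( (0.16 − 0.1386) / 0.0670 ) = Φ(0.32) = 62.5%.

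The arcsine formula is

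Φ( 2 × (arcsin√0.66 − arcsin√0.50) × √50 − 1.96 ) = Φ(0.343) = 63.4%.

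Both are consistent with about 63%. The documents name the software but not the formula, so the source of the 63% is an inference.

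**2. Rejection region of the planned test.** Because the null rate is 0.50, the binomial is symmetric and the two-sided exact p-value for k > 25 responders is 2 × P(Bin(50, 0.5) ≥ k).

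| Responders | Two-sided p | Exact 95% interval | Rejects? |
|---|---|---|---|
| 32/50 | 0.065 | 49.2% to 77.1% | no |
| 33/50 | 0.033 | 51.2% to 78.8% | yes |

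The test therefore rejects upward only at 33 or more. Its attained two-sided level is 3.3%.

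**3. Power of the planned test.** P(Bin(50, 0.66) ≥ 33) = 56.5%. The lower rejection region (17 or fewer) adds about 0.000004. Lowering the cut-off to 32 would give 67.7%, but 32/50 has p = 0.065 and does not reject. No whole-number cut-off at n = 50 gives 63%.

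**4. Sensitivity to n.** Exact power is saw-toothed:

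| n | Smallest rejecting count | Exact power at 66% |
|---|---|---|
| 45 | 30 | 53.2% |
| 49 | 32 | 60.6% |
| 50 | 33 | 56.5% |
| 51 | 33 | 63.9% |
| 52 | 34 | 60.0% |
| 53 | 35 | 56.1% |
| 54 | 35 | 63.3% |

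The mean over n = 50 to 59 is 62.4%.

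**5. Drop-out.** Assume that the 50 are counted before drop-out and that the section's 10% applies to them. With 45 evaluable subjects in the denominator, power is 53.2%. If instead the 10% count as non-responders (one of the possible sensitivity analyses in section 10.4.2), the effective rate is 0.66 × 0.90 = 59.4% and P(Bin(50, 0.594) ≥ 33) = 21.1%.

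**6. Checks at other values.** At the 80% response rate that section 10.5 cites from earlier trials, P(Bin(50, 0.80) ≥ 33) = 99.4%. For the main cohort, n = 150 rejects at 88 or more and the power at 66% is 97.5%, in line with the stated figure of more than 90%.

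**7. Retrospective power.** With n and the test fixed, power at the observed rate is a function of the observed count alone. At n = 50, 30 responders (p = 0.203) give 23.7%, 33 (p = 0.033) give 56.5%, and 36 (p = 0.003) give 86.4%. It re-expresses the p-value and carries no further information.

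**The case against.** The best defence is that 63% is not a slip of arithmetic. It is what standard approximations give, the text says approximately, and the sentence announcing an exact test governs the analysis and not necessarily the power calculation. The cohort is anticipated at 50 in one place and set as a minimum of 50 in another, and over 50 to 59 subjects the exact power averages 62.4%. On that view 56.5% is a low point on the sawtooth that one more subject would lift to 63.9%.

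Much of this is fair. The fault is a mismatch between the power method and the planned test, and 63% is a reasonable rough figure for a cohort somewhat above 50. It does not rescue the sentence as written, which ties the figure to only 50 subjects without saying that it comes from a method other than the planned test.

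It is also true that nothing depends on the number. Sections 10.4.2 and 10.5 call the cohort insufficiently powered, section 10.2 has no other formal hypothesis, and section 10.4.9 treats all but the primary endpoint as supportive. That limits the severity but does not make the figure right.

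The drop-out figures are conditional. The 21.1% in particular belongs to a sensitivity analysis that may or may not be run, and it is no evidence that 63% was miscalculated. The remark on retrospective power is a separate methods point that happens to sit in the same paragraph.

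**Conclusion.** The point holds and is minor. At the stated n of 50, true rate of 66% and two-sided 5% level, the planned exact test has 56.5% power, against the stated figure of about 63%. This rests only on inputs in sections 10.4.2 and 10.5 and on all 50 subjects having a 6-month outcome. If the 50 are treated subjects and 10% lack 6-month data and leave the denominator, the figure is 53.2%.

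The gap matters only if the true rate is near the planning value; at 80% the cohort has ample power. The main-cohort sample size, the primary analysis and the description of the stand-alone cohort as underpowered are unaffected.

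**What to change.** In section 10.5:

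- Replace the 63% with approximately 57%, labelled as the power of the exact two-sided 5% test with 50 subjects who have 6-month data. If the team prefers to keep 63%, label it as a large-sample approximation and print the exact figure beside it.
- State whether 50 is the number treated or the number with 6-month data. If it is the number treated, add that power is about 53% should 10% lack 6-month data and leave the denominator.
- Delete the sentence on retrospective power and interpret the stand-alone result through the exact 95% interval that is already planned.

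The cost is a text change: one figure restated, one clause added, one sentence removed. The main-cohort power statement needs no change.

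### Retrospective power planned for the stand-alone analysis only restates its p-value and can conflict with the exact confidence interval reported beside it

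*Combined protocol and SAP*

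**What the plan says.** Section 10.4.2 repeats the primary analysis in the Latera stand-alone population. It says in advance that the study is not powered for this subgroup, and that "the response rate, 95% confidence interval and p-value will be calculated".

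Section 10.5 gives the numbers: "The anticipated size of the Latera stand-alone Population is 50 subjects". The Protocol Summary words this as a minimum: "At least 50 subjects will have stand-alone Latera Implant procedure". Section 10.5 puts the prospective power at about 63% for a true response rate of 66%, calls this insufficient, and again plans the p-value and exact 95% interval. It then adds: "Retrospective power for the actual response rate will also be calculated for this comparison in order to contextualize the results".

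The actual response rate can only be the observed one. No section ties this calculation to a rate fixed in advance or says how the result is to be used. Section 10.2 states that there is no formal hypothesis beyond the primary efficacy endpoint. Section 10.4.9 treats everything other than the primary endpoint as supportive.

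**The concern.** Power describes a design at an assumed true rate. When the observed rate takes the place of the assumed one, the result is a transformation of the data already summarised by the p-value. It is low whenever the test fails and higher whenever it succeeds, whatever the true rate. It cannot answer the one question a reader would bring to it after a non-significant result: was the true rate near 50%, or was the cohort too small to show a higher one?

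The stand-alone population is the only analysis set in Section 10.3 defined by the absence of turbinate treatment, so readers interested in the implant without that co-treatment will look there. Appendix II says the data may support regulatory applications and publications. A figure that carries no information of its own, and that can suggest the opposite of the interval beside it, should not be pre-specified as context for that result.

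**Working it through.** **Inputs**, all from Section 10.5: n = 50 (anticipated); null hypothesis that "the proportion of responders at 6 months is =0.50, versus" a two-sided alternative; 5% two-sided level; design rate 66%; earlier observed rate 80%. On the test: "This hypothesis will be evaluated using an exact test".

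**Step 1. Reproduce the plan's power figure.** Normal approximation, with the null standard error for the critical value and the alternative standard error for power:

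Φ[(0.16 − 1.96 × √(0.25/50)) / √(0.66 × 0.34/50)] = Φ[(0.16 − 0.1386)/0.0670] = Φ(0.32) = 62.5%.

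The arcsine version gives 63.4%. Both agree with the stated 63%.

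**Step 2. Rejection region of the exact test.** P(X ≥ 33 | 50, 0.5) = 0.0164, within 0.025. P(X ≥ 32 | 50, 0.5) = 0.0325, above it. The test rejects at 33 or more responders and, by symmetry, at 17 or fewer. Results from 18 to 32 are non-significant. Exact power at 66% is 56.5%, and at 80% it is 99.4%.

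**Step 3. Observed power.** For x responders:

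- p(x) = 2 × P(X ≥ x | 50, 0.5) for x above 25, and 1 at x = 25
- observed power(x) = P(X ≥ 33 | 50, x/50) + P(X ≤ 17 | 50, x/50)

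| Responders | p-value | Observed power | Exact 95% CI |
|---|---|---|---|
| 25/50 | 1.00 | 3.3% | 0.355 to 0.645 |
| 28/50 | 0.480 | 10.0% | 0.413 to 0.700 |
| 30/50 | 0.203 | 23.7% | 0.452 to 0.736 |
| 31/50 | 0.119 | 33.5% | 0.472 to 0.753 |
| 32/50 | 0.065 | 44.7% | 0.492 to 0.771 |
| 33/50 | 0.033 | 56.5% | 0.512 to 0.788 |
| 35/50 | 0.0066 | 78.2% | 0.554 to 0.821 |
| 36/50 | 0.0026 | 86.4% | 0.575 to 0.838 |
| 40/50 | <0.0001 | 99.4% | 0.663 to 0.900 |

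Observed power rises as the p-value falls, with no exception. The test is symmetric about 50%, so 20/50 gives the same p-value and the same 23.7% as 30/50. The figure does not show direction either.

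**Step 4. Compare with the interval.** At 25/50 the 3.3% is simply the exact test's attained size (2 × 0.0164). It would read as a hopelessly small study, yet the interval's upper limit of 0.645 lies below 0.66, so the data speak against the planning assumption. More generally, the upper limit of every non-significant result is at most 0.771, so each would exclude the earlier 80% rate. Observed power shows neither fact.

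**Step 5. Sensitivity.** For assumed cohort sizes of 40, 45, 50, 55, 60 and 70, the highest observed power of a non-significant result is 44.1% to 45.5%, and the lowest for a significant one is 55.3% to 57.4%. If power is computed by the normal approximation of Step 1 instead, 32/50 gives 50.8% and 33/50 gives 62.5%. The ceiling moves; the dependence on the data already summarised by the p-value does not.

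**The case against.** The strongest reply is that little depends on this number. The subgroup is declared underpowered in advance, no formal hypothesis attaches to it, and the valid summary, the exact interval, is already planned in Sections 10.4.2 and 10.5. The primary mITT test, sample size, type 1 error and data collection are untouched. All of this stands and limits the weight of the point. It also means that deletion loses nothing.

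A reader might infer that the plan commits the sponsor to explaining a negative stand-alone result as underpowered. The documents do not support this. They say only that the figure gives context; they set no rule of interpretation. What is automatic is the low number after a non-significant test, not the use made of it.

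Nor does deletion remove every statement about low power. Sections 10.4.2 and 10.5 keep their prospective statements, and these are legitimate because they use a rate fixed in advance.

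A reader might also infer that stand-alone response can be credited to the implant. The set removes turbinate co-treatment, but Sections 10.4.1 and 10.6 describe a single-arm, open-label study without randomisation or blinding, so natural change and placebo response remain.

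Finally, a non-significant result may be unlikely. At n = 50 the exact test fails in about 43% of trials if the true rate is 66% (100 − 56.5), but in about 0.6% if it is 80% (100 − 99.4). That bears on how often the figure would mislead, not on whether it is informative.

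**Conclusion.** The point holds as a defect in one planned calculation. Retrospective power at the observed rate is uninformative beyond the p-value. At n = 50 with exact power, it is at most 44.7% for every non-significant result and at least 56.5% for every significant one. It can contradict the exact interval, as 25/50 shows. The ceiling assumes that the anticipated cohort size, the exact two-sided 5% test and exact power are used; the lack of added information does not depend on those choices.

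The consequence is confined to the interpretation of a supportive subgroup. The primary conclusion is not at risk, and the documents do not show that any particular reading of the figure is intended.

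**What to change.** Delete the retrospective-power sentence from Section 10.5 and keep it out of the SAP, which Section 10.1 says will be finalised before database lock. Suggested replacement: *The stand-alone result will be interpreted from its exact 95% confidence interval, stating whether the interval excludes 50% and whether it includes the planned 66%. Power will be quoted only at response rates fixed in advance.*

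Section 10.4.2 needs no change, because the response rate, interval and p-value it lists are the right quantities. If the prospective power is restated, note that 63% matches a normal approximation, while the exact test named in the plan gives 56.5%.

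The cost is one sentence in Section 10.5 and the corresponding text in the SAP. No data collection, subject burden or sample size changes.
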